9.8.7 Additional Analyses

Additional analyses will explore the potential modifying effects of baseline measures on the changes in primary and secondary efficacy outcomes. These measures will include age, gender, baseline severity, and other diagnoses/co-morbidities. The analyses will specifically test for differential changes across the subgroups defined by the potential modifiers using general linear models. Further analyses will explore changes in the

subscales of some of the efficacy measures, for example the six major life domains of the total WHODAS score.

9.9 Missing Data

Efficacy measures are not assessed after a participant discontinues adalimumab. The exception to this will be the analysis of proportion of patients at 6 months who remain on adalimumab, having satisfied the requirements for application for renewal of subsidy by special authority. Any participants for whom this assessment is not available will be assumed to have not met these requirements. There will be no other imputation for missing data.

9.10 Interim Analysis

An interim analysis will be conducted at the time point indicated in the study milestones section (6.0) on data from all patients who have completed the study up to and including the 6 month time-point. This analysis will analyse and summarise the changes in the primary and secondary efficacy endpoints and the safety data. The results of this analysis will not influence the ongoing conduct of the study.

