9.0 Research Methods

9.1 Study Design

This is a Phase IV, parallel-group, observational, multicentre study designed to investigate the effectiveness of adalimumab on health and disability outcomes in New Zealand patients diagnosed with rheumatoid arthritis, Crohn's disease and psoriasis.

The decision to commence treatment with adalimumab is to be made by the patient and the physician before including the patient in this study and has to be clearly separated and independent of the decision to include the patient in the study.

Overall, a minimum of approximately 190 subjects with these three IMIDs are planned to be enrolled in the study at up to 15 sites. Approximately 80 subjects will be enrolled into each of 2 parallel study groups of patients diagnosed with rheumatoid arthritis or Crohn's disease. A minimum of 30 subjects with psoriasis will also be enrolled. All subjects will receive at least 3 months of treatment with adalimumab. AbbVie is not supplying adalimumab; adalimumab is to be used according to the approved adalimumab New Zealand Datasheet and is to be prescribed by the physician under usual and customary practice of physician prescription. Continuation of adalimumab will depend upon the patient meeting the disease-specific response criteria as determined by the investigator

between 3 and 6 months, which will allow continuing reimbursement of drug supply under “Special Authority”.

To assess health and disability outcomes, the WHODAS 2.0 score will be assessed at baseline, 2, 4 and 6 months after treatment initiation with adalimumab. Work productivity will be assessed at these time points using the WPAI:GH V2.0 (8). Psychological distress will be measured using the K10 scale (9). Subject happiness will also be measured, Flourishing Scale (10), Subject Vitality Scale (11). Disease-specific patient reported outcomes (PROs) that are more commonly used in clinical practice; Health Assessment Questionnaire–Disability Index (HAQ-DI) (12), Short Inflammatory Bowel Disease Questionnaire (SIBDQ) (13), Dermatology Life Quality Index (DLQI) (14) will also be assessed. Variations of these disease-specific indices were used in some of the pivotal Phase III studies for adalimumab.

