Each subject has the right to withdraw from the study at any time. In addition, the investigator may discontinue a subject from the study at any time if the investigator considers it necessary for any reason, including the occurrence of an adverse event. If the reason for treatment discontinuation is due to a serious adverse event, it should be reported to AbbVie within 24 hours of physician's awareness.

In the event that a subject withdraws or is discontinued from the study, the primary reason for discontinuation and any other reason(s) for the discontinuation from the study will be recorded. Following discontinuation of the study drug, the patient will be treated in accordance with the Investigator's best clinical judgment.

For subjects who discontinue from the study prematurely a phone call will be made 30 days after the last dose of adalimumab is administered to obtain follow-up information on any ongoing or new adverse events.

Subjects will be withdrawn from the study immediately if any of the following occur:

- The investigator believes it is in the best interest of the subject.
- The subject or subject's guardian requests withdrawal from the study.
- A selection criteria violation was noted after the subject started study drug.

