9.8 Data Analysis

9.8.1 Definitions

9.8.1.1 Participant Population

All participants who are recruited into the study and start study medication will be used for analysis. A full analysis set will be used for the analysis of the efficacy outcomes with all available data used for the analyses of each outcome at the relevant time points. Efficacy measures are not assessed after a participant discontinues adalimumab. The exception to this will be the analysis of proportion of patients at 6 months who remain on adalimumab, having satisfied the requirements for application for renewal of subsidy by Special Authority. Any participants for whom this assessment is not available will be assumed to have not met these requirements. The primary population for the evaluation of study safety objectives will be the safety population, defined as all participants enrolled into the trial who started study medication. Safety outcomes will only be considered while the patient is on adalimumab. A standard consort diagram describing participant flow (including loss to follow-up and discontinuations for any reason) through the study will be generated.

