9.8.1.2 Observational Period

The observational period will be from participant enrolment to 6 months or until any participant stops study medication or withdraws from the study.

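### Section 9.10 limits the interim efficacy and safety summaries to month-6 completers, so early discontinuations, the adverse events behind them and their month-2 and month-4 WHODAS values are left out

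*Combined protocol and SAP*

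**What the plan says.** Section 9.10 (Interim Analysis) conducts the interim "on data from all patients who have completed the study up to and including the 6 month time-point". It gives the content in one sentence, "This analysis will analyse and summarise the changes in the primary and secondary efficacy endpoints and the safety data", and then states: "The results of this analysis will not influence the ongoing conduct of the study". It names no separate safety set and has no clause for people who left early.

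The general analysis rules are in 9.8.1.1 (Participant Population). Everyone recruited who starts medication is analysed, with "all available data used for the analyses of each outcome at the relevant time points". The safety population is "defined as all participants enrolled into the trial who started study medication". Section 9.8.6 (Safety Analyses) plans a listing and summary of adverse events that led to discontinuation. Section 9.8.5 (Secondary Efficacy Analyses) includes the WHODAS change at months 2 and 4.

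Three provisions bear on who can complete:

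- 9.8.1.2, on when observation ends: "The observational period will be from participant enrolment to 6 months or until any participant stops study medication or withdraws from the study".
- 9.2.3 (Discontinuation of Individual Subjects): the investigator may discontinue a subject "if the investigator considers it necessary for any reason, including the occurrence of an adverse event".
- 9.1 (Study Design): "Continuation of adalimumab will depend upon the patient meeting the disease-specific response criteria as determined by the investigator", with that decision falling between 3 and 6 months.

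**The concern.** Membership of the interim set depends on something that happens after treatment starts and is related to tolerability and response. A participant who has an adverse event at month 1 and is discontinued does not complete month 6, so neither the participant nor the event appears in the interim safety summary. A reader who sees few or no adverse events leading to discontinuation could take that as good tolerability, when the selection rule produced it.

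For efficacy, a participant who gives WHODAS scores at months 2 and 4 and then stops at month 5 contributes both scores under 9.8.1.1 but neither at the interim. The interim and final figures for the same endpoint would then rest on differently selected people. The Interim Report is a planned milestone (31 March 2016 in section 6.0), so these figures will be read.

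**Working it through.** The documents state no figure for this point, so the check compares the rules first and then illustrates size under stated assumptions.

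**1. Who is in which set, as written**

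| Participant | 9.8.1.1 rules | Interim under 9.10 |
|---|---|---|
| Completes month 6 on drug | Safety: in. Efficacy: all visits | In |
| Withdrawn or discontinued from the study before month 6 | Safety: in. Efficacy: visits up to leaving | Out |
| Stops adalimumab before month 6 | Safety: in. Efficacy: visits up to stopping | Out, because 9.8.1.2 ends observation at stopping |

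The last row has one qualification. The Abstract (4.0, Data Analysis) compares the month-6 WHODAS change with that of patients not continuing, which implies that some may be followed off drug. Sections 9.8.1.1 and 9.9 say efficacy is not assessed after stopping. This is why the interim summary of events leading to discontinuation is described as empty or nearly so.

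**2. Which endpoints differ between interim and final**

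- Safety: differs, with no conflicting text.
- WHODAS at months 2 and 4: differs. The Abstract's restriction to continuing patients does not list these time points for WHODAS.
- Disease-specific indices, WPAI:GH, K10, Flourishing and Vitality scales at months 2 and 4: differ only if 9.8 overrides the Abstract, which limits these changes to patients continuing on adalimumab.
- WHODAS at month 6: no contrast. Under 9.8 and 9.9 it is measured only on drug in the final analysis too.

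**3. Shift in a month-2 or month-4 mean (assumed inputs)**

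Let s be the share of those with a value who stop before month 6, and d the amount, in SD of change, by which their mean improvement falls short of the completers' mean m.

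- All-available mean = (1 − s)m + s(m − d) = m − s × d, so the completer mean is too favourable by s × d.
- s = 0.10, d = 0.25: 0.025 SD.
- s = 0.20, d = 0.50: 0.10 SD.
- s = 0.30, d = 0.75: 0.225 SD.

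**4. Adverse event percentages (assumed inputs)**

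Suppose completers have a 10% risk and stoppers two to three times that.

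- 10% stopping: 0.9 × 10% + 0.1 × 20% = 11%, or with 30% in stoppers, 12%.
- 40% stopping: 0.6 × 10% + 0.4 × 20% = 14%, or with 30% in stoppers, 18%.

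The interim would show 10% in every case.

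**5. How many people this concerns**

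Section 6.0 gives first visit on 06 July 2015, interim lock on 01 March 2016 and end of data collection on 06 September 2016: 239 and 428 days after first visit. Assume 183 days of follow-up, uniform accrual and the minimum of 190 participants.

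- Accrual period: 428 − 183 = 245 days.
- Enrolment days that allow month 6 by the lock: 239 − 183 = 56.
- Participants: 190 × 56/245 ≈ 43.
- At 20% stopping, about 9 are left out and 35 remain. The standard error of a mean change is then about 1/√35 = 0.17 SD.

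**The case against.** **Completion may mean elapsed time.** Section 9.10 could have been meant as a data cut, taking those whose six months are over, with 9.8.1.1 applied on top; 9.8.1.1 is not labelled as a rule for the final analysis only. This is possible, but the text says completed, and nothing restores those who left. If elapsed time was meant, the proposed wording simply confirms it.

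**The Abstract already restricts efficacy to continuing patients.** This stands for the questionnaires other than WHODAS, where the contrast is conditional. It does not reach safety or WHODAS at months 2 and 4.

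**The size is assumed and may be small.** This stands. Both s and d are assumptions, and the central 0.10 SD is below the illustrative standard error of 0.17 SD. A reader might infer that those left out are mostly non-responders. The documents do not show this: they give no stopping rate or split of reasons, 9.2.3 allows discontinuation for any reason, and a response decision made close to month 6 may concern someone who has already completed. A reader might also scale the shift against the 0.40 effect size in 9.6. That figure is a detectable effect within the rheumatoid arthritis and Crohn's groups separately, not an expected pooled change at month 2 or 4, so the ratio would say little.

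**The renewal proportion would be inflated.** A reader might infer this because stoppers leave the denominator. Section 9.10 speaks only of changes, so the proportion may not be reported at the interim at all.

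**Nothing depends on the interim.** Conduct is not influenced and serious adverse events are notified individually within 24 hours (11.5). This limits the consequence but does not make the report's figures representative.

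**Conclusion.** The point holds for section 9.10 as written. It is firmest for safety: the interim set contradicts the all-starters safety population and removes, by construction, nearly all events that led to discontinuation before month 6. It also holds for WHODAS at months 2 and 4. For the other questionnaires it depends on 9.8 overriding the Abstract, and those two passages must be reconciled in any case.

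The direction is probably favourable to adalimumab, because continuation depends partly on response. The size cannot be known from the documents; the 0.025 to 0.225 SD range rests entirely on assumed s and d.

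A reader might infer that the study's conclusions are biased. The documents do not support that: the interim does not influence conduct, and the final analysis sets are untouched. The matter is worth correcting because it would mislead readers of one planned report and takes only a few sentences to put right.

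**What to change.** In 9.10, replace the completer criterion with this set: all participants who started adalimumab and whose scheduled month-6 date, plus the 7-day visit window, has passed by the interim cut-off, whether or not they continued or withdrew. Then state that:

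- the 9.8.1.1 rules apply to that set, with all available data at each time point and a safety population of all starters in it;
- adverse events leading to discontinuation are included;
- if the renewal proportion is reported, an unavailable assessment counts as not met, as in 9.9.

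Reconcile the Abstract with 9.8 on whether the questionnaire changes are limited to continuing patients.

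The cost is a few sentences, slightly more data cleaning before the interim lock, and possibly less favourable interim figures. Participants whose month-6 date falls in the last 7 days before the cut-off move to the final report. Under the accrual assumptions above, the date-eligible set is 190 × 49/245 = 38 instead of about 43, so about 5 move. The resulting set of 38, stoppers included, is about as large as the 35 completers left at 20% stopping.

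Treatment, visits and the final analysis do not change.

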9.11 Quality Control

Steps to be taken to ensure the accuracy and reliability of data include the selection of qualified investigators and appropriate study centres, review of protocol procedures with the investigator and associated personnel before the study and periodic monitoring visits by the sponsor. Written instructions will be provided for administration and collection of study questionnaires.

Guidelines for CRF completion will be provided and reviewed with study personnel before the start of the study. The sponsor will review CRFs and subject questionnaires for accuracy and completeness during on-site monitoring visits and after transmission to the sponsor; any discrepancies will be resolved with the investigator or designee, as appropriate. After upload of the data into the clinical study database they will be verified for accuracy and consistency with the data sources.

9.12 Limitations of the Research Methods**9.13 Other Aspects****9.13.1 Note To File**

The Principal Investigator or designee will be responsible for documenting study relevant information and occurrences that affects the course of the study. The information and occurrences are not protocol deviations but will be documented in a note to file and will be communicated to the sponsor.

9.13.2 Training Log

All designated study personnel must be trained on the study protocol and procedures. Training and retraining are documented on the Training Log.

9.13.3 Visitor Log

All Sponsor or other related individuals who visit the study site must sign the Visitor Log.

9.13.4 Responsibilities of the Principal Investigator

The Principal Investigator is responsible for oversight of enrollment, the patient consent process, study related procedures, compliance with the protocol, all institutional, state and local guidelines.

It is the responsibility of the Principal Investigator to select, supervise, and delegate responsibility for study conduct to staff members. The Principal Investigator is responsible for determining the appropriate staff qualifications required for specific study-related tasks to be delegated. Study-related tasks delegated to staff members will be documented on the Site Signature and Delegation Log.

9.13.5 End of Trial

End of Trial is defined as last subject's last visit (LPLV).

10.0 Protection of Human Subjects

This study must be conducted in compliance with the recommendations of the Declaration of Helsinki, 2008 (World Medical Association). In addition, this study will adhere to all general and local legal and regulatory requirements applicable to non-interventional studies.

Informed consent will be obtained from each subject before the subject can participate in the study. The contents and process of obtaining informed consent will be in accordance with all applicable regulatory requirements.

As required by applicable local regulations, the sponsor's Regulatory Affairs group will ensure all legal regulatory aspects are covered, and obtain approval of the appropriate regulatory bodies, prior to study initiation in regions where an approval is required.

This study is non-interventional and falls outside the scope of the EU Directive 2001/20/EC, the EU Directive 2005/28/EC and International Conference on Harmonization (ICH) Good Clinical Practice (GCP) guidelines.

This study complies with the EU Directive 95/46/EC of the European Parliament and of the Council of 24 October 1995 on the protection of individuals with regard to the processing of personal data and on the free movement of such data.

11.0 Management and Reporting of Adverse Events/Adverse Reactions

11.1 Adverse Event Definition and Serious Adverse Event Categories

An adverse event (AE) is defined as any untoward medical occurrence in a patient, which does not necessarily have a causal relationship with their treatment. An adverse event can therefore be any unfavorable and unintended sign (including an abnormal laboratory finding), symptom, or disease temporally associated with the use of a medicinal product, whether or not the event is considered causally related to the use of the product.

Such an event can result from use of the drug as stipulated in the labeling, as well as from accidental or intentional overdose, drug abuse, or drug withdrawal. Any worsening of a pre-existing condition or illness is considered an adverse event.

An elective surgery/procedure scheduled to occur during the study will not be considered an adverse event if the surgery/procedure is being performed for a pre-existing condition and the surgery/procedure has been pre-planned prior to study entry. However, if the pre-existing condition deteriorates unexpectedly during the study (*e.g.*, surgery performed

earlier than planned), then the deterioration of the condition for which the elective surgery/procedure is being done will be considered an adverse event.

If an adverse event meets any of the following criteria, it is considered a serious adverse event (SAE):

Death of Patient:	An event that results in the death of a patient.
Life-Threatening:	An event that, in the opinion of the investigator, would have resulted in immediate fatality if medical intervention had not been taken. This does not include an event that would have been fatal if it had occurred in a more severe form.
Hospitalization:	An event that results in an admission to the hospital for any length of time. This does not include an emergency room visit or admission to an outpatient facility.
Prolongation of Hospitalization:	An event that occurs while the study patient is hospitalized and prolongs the patient's hospital stay.
Congenital Anomaly:	An anomaly detected at or after birth, or any anomaly that results in fetal loss.
Persistent or Significant Disability/Incapacity:	An event that results in a condition that substantially interferes with the activities of daily living of a study patient. Disability is not intended to include experiences of relatively minor medical significance such as headache, nausea, vomiting, diarrhea, influenza, and accidental trauma (e.g., sprained ankle).
Important Medical Event Requiring Medical or Surgical Intervention to Prevent Serious Outcome:	An important medical event that may not be immediately life-threatening or result in death or hospitalization, but based on medical judgment may jeopardize the patient and may require medical or surgical intervention to prevent any of the outcomes listed above (i.e., death of patient, life threatening, hospitalization, prolongation of hospitalization, congenital anomaly, or persistent or significant disability/incapacity). Additionally, any elective or

spontaneous abortion or stillbirth is considered an important medical event. Examples of such events include allergic bronchospasm requiring intensive treatment in an emergency room or at home, blood dyscrasias or convulsions that do not result in inpatient hospitalization, or the development of drug dependency or drug abuse.

11.2 Severity

The following definitions will be used to rate the severity for any adverse event being collected as an endpoint/data point in the study and for all serious adverse events.

- Mild:** The adverse event is transient and easily tolerated by the patient.
- Moderate:** The adverse event causes the patient discomfort and interrupts the patient's usual activities.
- Severe:** The adverse event causes considerable interference with the patient's usual activities and may be incapacitating or life threatening.

11.3 Relationship to Pharmaceutical Product

The following definitions will be used to assess the relationship of the adverse event to the use of product:

- Reasonable Possibility** An adverse event where there is evidence to suggest a causal relationship between the product and the adverse event.
- No Reasonable Possibility** An adverse event where there is no evidence to suggest a causal relationship between the product and the adverse event.

If no reasonable possibility of being related to product is given, an alternate etiology must be provided for the adverse event.

